**Intervention protocol and analysis**

**Date :24/2/2025**

**[name]**

**NCT07069621**

**Intervention Protocol**

The Positive Parenting Program (Triple P), developed by Sanders et al. (2008) at the University of Queensland, Australia, is an evidence-based intervention designed to enhance parent-child interactions. The program equips mothers and caregivers with effective strategies to mitigate behavioural problems in children while boosting their confidence and parenting skills (Ashori, 2023).

An online course from the Triple P Association in Britain was completed by the researcher, leading to an accredited certificate to train in Triple P Level 4(Appendix 4), specifically tailored for children with special needs. The core content for the sessions was sourced from the Triple P provider website and supplemented by additional materials, which the researcher translated into Arabic from Every Parent manual, a key resource in the Triple P curriculum. Each subtopic was reinforced with Arabic-language videos from the Triple P program, shown during the sessions to illustrate key concepts and skills.

The program began with an introductory session, which covered the program's objectives, established a trusting relationship with the participants, and secured informed consent. During this session, demographic data was collected, and pre-intervention questionnaires were completed by the mothers. The implementation of Triple P consisted of multiple sessions including the major subtopic contents of group triple p covered for the participants (Table 3.1), each lasting approximately two hours, covering program strategies, videos, discussions, and follow-up tasks. Mothers received individual phone calls lasting 30-50 minutes, two to three times after the program to reinforce the practical application of Triple P strategies for managing their children's behaviour and to help troubleshoot any challenges. Daily support was provided through short messages and videos via WhatsApp groups, ensuring ongoing engagement with the program content, using prompts

during the phone call conversation for correcting the management skills learned in the sessions in a real-world situations with their children, and questions about how would the situation would be handled next time in terms of gaining self-agency skill in child disruptive behaviour management. Pre- and post-intervention assessments were conducted to measure outcomes for each participant. Simultaneously, the control group underwent pre-testing, with post-testing conducted two months later to assess comparative outcomes.

Table 3.1Contents of group triple p sessions Adapted from (Yusuf, Ö., et al,2019).

Session number	Content	Session duration
1. Positive parenting	Working as a group What is positive parenting? Why do children behave as they do? Goals for change Keeping track Developing good relationships with children Encouraging good behaviour Teaching new skills and behaviours Managing misbehaviour Developing parenting routines Finalizing your behaviour chart Family survival tips High-risk situations Planned activities Preparing for telephone sessions Preparing for the session Update on practice Other issues	120 minutes (group)
2. Helping children develop	Developing good relationships with children Encouraging good behaviour	120 minutes (group)
3. Managing misbehaviour	Teaching new skills and behaviours Managing misbehaviour Developing parenting routines Finalizing your behaviour chart	120 minutes (group)
4. Planning ahead	Family survival tips High-risk situations Planned activities Preparing for the session Update on practice Other issues	120 minutes (group)
5. Using positive parenting strategies 1	Preparing for the session Update on practice Other issues	15–30 minutes (telephone)
6. Using positive parenting strategies 2	Preparing for the session Update on practice Other issues	15–30 minutes (telephone)
7. Using positive parenting strategies 3	Preparing for the session Update on practice Other issues	15–30 minutes (telephone)
8. Programme close	Preparing for the session Update on practice Phasing out the programme Progress review Keeping up the good changes Problem-solving for the future Future goals Final assessment	120 minutes (group)

## **Ethical consideration**

Ethical approval for the study was obtained from the AAUP Review Board (Appendix1), and additional approval was granted by the Ministry of Health (Appendix5) for access to information from medical files. Informed consent (Appendix3) was obtained from each participant, and all outcome measures were collected anonymously. Participation in the study was entirely voluntary, with participants given the option to withdraw at any time. To ensure confidentiality, all collected data was securely stored in a locked environment accessible only to the researcher.

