## **Data Analysis**

All statistical analyses were conducted using IBM SPSS Statistics version 27. Data were first screened for completeness and accuracy. Missing data were assumed to be random of less than 3%, and were excluded using listwise deletion. Descriptive statistics (frequencies, percentages, means, and standard deviations) were used to characterize demographic variables and baseline measures. Reliability for each outcome instrument was assessed using Cronbach's alpha coefficients and intraclass correlation coefficients (ICC). Normality of continuous variables was evaluated using the Kolmogorov-Smirnov test. To assess baseline equivalence between the intervention and control groups, independent samples *t*-tests were performed on all pre-intervention variables. The effectiveness of the Triple P intervention was analyzed by comparing pre- and post-intervention scores within and between groups using independent *t*-tests. Statistical significance was determined at an alpha level of 0.05 (two-tailed). The primary analyses focused on evaluating changes in parenting practices, parental competence, and child behavior. Differences in mean change scores between the two groups were used to assess the impact of the intervention relative to standard care. Sensitivity or subgroup analysis was not conducted.

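### Outcomes are described as anonymous with no linking code given, yet the effect is judged on change scores, and an independent t-test is named for the paired within-group comparison

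*Combined protocol and SAP*

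**What the plan says.** On collection, the Ethical consideration section states that "all outcome measures were collected anonymously". It mentions locked storage with access for the researcher only, but no study number, self-generated code or linking key.

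On measurement, the Intervention Protocol section says "Pre- and post-intervention assessments were conducted to measure outcomes for each participant", and that "the control group underwent pre-testing, with post-testing conducted two months later to assess comparative outcomes".

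On analysis, the Data Analysis section gives the effect measure: "Differences in mean change scores between the two groups were used to assess the impact of the intervention relative to standard care". It describes the tests as "comparing pre- and post-intervention scores within and between groups using independent *t*-tests". No paired test is named anywhere. On missing data it says "Missing data were assumed to be random of less than 3%, and were excluded using listwise deletion", without saying whether deletion applies within a time point or across both.

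**The concern.** A change score belongs to one mother, and computing it means putting her two forms side by side. If the forms carried nothing that identified her, that cannot be done, and the test on which the treatment effect rests has no data to work on. The same holds for removing a mother from both time points when one of her forms is missing.

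The second problem does not depend on how the forms were collected. The within-group comparison sets the same mothers' scores before and after against each other, and the test named for it treats them as two separate sets of people. Followed literally, the plan gives that comparison the wrong standard error even if every form was coded.

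At stake are the precision reported for the change analyses and the reader's ability to tell which dataset lies behind the main result.

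**Working it through.** **No figure to reproduce.** The documents give no sample size, standard deviation, effect size or pre-post correlation. The check is therefore algebraic, with r assumed over a range and the pre and post standard deviations both taken as s.

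**Step 1: what needs linkage.** Mean change = mean(post) − mean(pre). If the same mothers complete both forms, this value is the same whether or not the forms are matched. In a simulated set of 30 pairs, shuffling the post scores left the mean change at 0.0011 but moved the standard deviation of change from 0.851 to 1.144. So the point estimate survives without linkage, but the standard error of individual change does not.

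**Step 2: size of the error.**
- Matched pairs: Var(change) = 2s²(1 − r).
- Treated as independent: 2s².
- Ratio of standard errors: √[2s² / 2s²(1 − r)] = 1/√(1 − r).

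**Step 3: comparison with a post-test-only analysis.** This needs no linkage and has variance s² per mother. Its standard error relative to matched change is √[s² / 2s²(1 − r)] = 1/√[2(1 − r)].

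| Assumed r | SD of matched change, in units of s | SD if treated as independent | SE ratio, independent to matched | SE ratio, post-test only to matched change |
|---|---|---|---|---|
| 0.3 | 1.183 | 1.414 | 1.20 | 0.85 |
| 0.5 | 1.000 | 1.414 | 1.41 | 1.00 |
| 0.6 | 0.894 | 1.414 | 1.58 | 1.12 |
| 0.7 | 0.775 | 1.414 | 1.83 | 1.29 |
| 0.8 | 0.632 | 1.414 | 2.24 | 1.58 |

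**Step 4: direction of the error.** An independent t-test on paired data with no true change was simulated 20,000 times with an assumed 30 mothers. At the plan's nominal two-sided 0.05 it rejected in about 0.049 of runs at r = 0, 0.019 at r = 0.3, 0.007 at r = 0.5 and 0.0006 at r = 0.7. With positive correlation the test rejects too seldom.

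**Step 5: what matching would add.** Adjusting the post-test score for the pre-test score leaves variance s²(1 − r²). Relative to change scores this is (1 − r²) / [2(1 − r)] = (1 + r)/2, which is 0.75 at r = 0.5 and 0.85 at r = 0.7. Adjustment is therefore more precise than change scores for any r below 1.

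**The case against.** The strongest reply is that one word in an ethics paragraph is being asked to carry too much. Beside statements on confidentiality and storage, anonymous may only mean that no names were on the forms. The reference to outcomes for each participant, and the use of change scores at all, fit coded forms. The consent form and the ethics approval are cited as appendices and were not available for review, and either could describe a code. This stands: the documents do not establish that the forms were unlinked.

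A reader might infer that the planned analysis cannot be run at all. The documents do not support that. With complete data the difference in mean change can be estimated without matching, and the independent t-tests that are named can be computed on forms labelled only by group and time. What would fail without linkage is the test on individual change scores, and listwise deletion if it was meant to run across both time points.

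A reader might also take the independent t-tests as evidence that the data were unlinked. That is weak. One sentence covers within-group and between-group comparisons together, and an independent t-test is the right test for change scores between groups. A paired test may simply not have been named.

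Two further points stand. No baseline-adjusted analysis is planned, so losing it would be a missed option, not a broken step. And if forms cannot be matched, the fair alternative is a post-test comparison, against which the loss is nil at r = 0.5 and 1.12 and 1.29 times at r = 0.6 and 0.7.

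None of this removes the conflict between the two sections, or makes an independent t-test correct for the same mothers measured twice.

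**Conclusion.** The concern holds in a limited form. The documents describe anonymous collection and no linking code in the text available, base the effect on change scores, and name an independent test for a paired comparison. A reader cannot tell whether the change-score test was possible, and the within-group test is wrong as written in either case.

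Ignoring the pairing overstates the standard error by 1.41 times at r = 0.5 and 1.83 times at r = 0.7. This assumes equal pre and post standard deviations and the same mothers at both times, and the r values are assumptions. The error costs power and does not create false positives when r is positive. It should not be read as showing that the trial's effect estimate is biased or that the data were in fact unlinkable.

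**What to change.** Reconcile the Ethical consideration and Data Analysis sections by stating whether the forms carried a code and how each mother's pre and post forms were matched. Then take one of two routes.

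- **If the forms can be matched:** use a paired t-test for the within-group comparison and an independent t-test on individual change scores between groups or, better, compare post-test scores adjusted for the pre-test score. Say that listwise deletion is applied to matched pairs, if that is what was meant.
- **If they cannot be matched:** withdraw the change-score test and report the between-group post-test comparison, to be read alongside the baseline comparison already planned. This requires only that each form shows group and time point.

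The cost is a few sentences and a rerun of the affected tests. Data collection is described in the past tense, so adding codes to forms or rewording consent is no longer a remedy; the text should report what was actually done. One small downside of the first route is that the data would be described as coded instead of anonymous, which needs a line in the ethics file.

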## **Pilot Testing**

A pilot testing was conducted to assess the feasibility of Triple P program implementation with a small group of mothers whose children have ADHD. The administration and implementation of the Triple P program for these mothers were tested for its acceptance and approval in a different cultural context from its Western origins. The program was tailored according to the cultural and regional circumstances of the Middle East. The pilot study received full review and approval from the institutional review board of the AAUP, as well as the recruitment setting. Written informed consent was obtained from all participants and as an agreement of being involved in the study, 10 participants were conveniently selected to have the triple p sessions in the pilot study. Participants were contacted by telephone to join the study after obtaining permission and approval from the Ministry of Health to access child mental health clinic records, mothers were randomly selected from the clinic's registry of children receiving follow-up care and medication (Concerta, which is Methylphenidate, a CNS stimulant that inhibits the reuptake of dopamine and norepinephrine, approved for treating ADHD). All sessions were held in full equipped meeting rooms, satisfactory outcomes were obtained by the participants for the administration of the program, minor changes for the PS were introduced by using the shortened version, with the addition of online sessions for more convenience for the mothers as they all agreed on, participants in the pilot included in the study sample, as no change occurred in the study methodology.

## **Data Analysis**

All statistical analyses were conducted using IBM SPSS Statistics version 27. Data were first screened for completeness and accuracy. Missing data were assumed to be random of less than 3%, and were excluded using listwise deletion. Descriptive statistics (frequencies, percentages, means, and standard deviations) were used to characterize demographic variables and baseline measures. Reliability for each outcome instrument was assessed using Cronbach's alpha coefficients and intraclass correlation coefficients (ICC). Normality of continuous variables was evaluated using the Kolmogorov-Smirnov test. To assess baseline equivalence between the intervention and control groups, independent samples *t*-tests were performed on all pre-intervention variables. The effectiveness of the Triple P intervention was analyzed by comparing pre- and post-intervention scores within and between groups using independent *t*-tests. Statistical significance was determined at an alpha level of 0.05 (two-tailed). The primary analyses focused on evaluating changes in parenting practices, parental competence, and child behavior. Differences in mean change scores between the two groups were used to assess the impact of the intervention relative to standard care. Sensitivity or subgroup analysis was not conducted.

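### The Data Analysis section leaves an uncontrolled within-group pre/post test standing as evidence of Triple P effectiveness beside the valid between-group contrast, and does not say which one decides.

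*Combined protocol and SAP*

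**What the plan says.** Four statements in the Data Analysis section bear on this.

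- Effectiveness: "The effectiveness of the Triple P intervention was analyzed by comparing pre- and post-intervention scores within and between groups", with independent t-tests as the named method. The two comparisons are named together and neither is ranked.
- Threshold: "Statistical significance was determined at an alpha level of 0.05 (two-tailed"). It is not restricted to the between-group test.
- Primary analyses: "The primary analyses focused on evaluating changes in parenting practices, parental competence, and child behavior". The sentence does not say whether the change is within or between groups.
- Controlled contrast: "Differences in mean change scores between the two groups were used to assess the impact of the intervention relative to standard care".

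The Intervention Protocol section describes a concurrent comparator: "the control group underwent pre-testing, with post-testing conducted two months later to assess comparative outcomes". On background care, the Pilot Testing section says that "mothers were randomly selected from the clinic's registry of children receiving follow-up care and medication", and that pilot participants were kept in the study sample.

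**The concern.** A pre-to-post change in the Triple P arm is the programme's effect plus whatever would have changed anyway. The control group is there to remove the second part, and a within-group test makes no use of it.

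The documents themselves point to two sources of shared change: continuing clinic care (the comparator is standard care) and repeated completion of the questionnaires, since both arms are tested before and after. Natural course and regression to the mean are possible, but the documents give no severity-based entry rule and no figures from which to size them.

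What is at stake is the main conclusion on each outcome. If the within-group result is significant and the between-group result is not, the text does not say what is to be concluded. A report could cite the former, or the pattern of a significant change in Triple P and a non-significant one in controls, as support for effectiveness when the true effect is zero.

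**Working it through.** **What each comparison estimates.** Let s be the change shared by both arms and τ the Triple P effect.

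- Within the Triple P arm: mean(post) − mean(pre) estimates s + τ.
- Between groups: (s + τ) − s = τ.

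With τ = 0, the within-group test is a test of s. The between-group test is unaffected by s.

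**Inputs from the documents.** Two-sided alpha of 0.05 (z = 1.96). This is the only relevant figure given; there is no sample size, SD, correlation or effect size, so no figure of the plan's own can be reproduced.

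**Assumed inputs, for illustration.** n = 30 or 50 per arm; pre-post correlation ρ = 0.5 or 0.7; the same s = 0.2, 0.3 or 0.4 SD in both arms; τ = 0; one outcome; normal scores with SD 1 at both times.

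**Formulas.**

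- Paired test: non-central t with n − 1 degrees of freedom and non-centrality s√n / √(2(1 − ρ)).
- Independent t-test on pre versus post, as the plan names it: the statistic is centred near s√(n/2) with spread of about √(1 − ρ) rather than 1, because the test ignores the correlation. Rates come from 20,000 simulated trials per setting.
- Significant in Triple P and not in control: p(1 − p), where p is the within-arm rate, because the arms are independent. This cannot exceed 0.25.

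**Worked example (n = 30, ρ = 0.5, s = 0.3).**

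- Paired: SD of change = √(2 × 0.5) = 1; non-centrality = 0.3 × √30 = 1.64; critical t = 2.045; rate 36%; p(1 − p) = 0.36 × 0.64 = 23%.
- Independent: centre = 0.3 × √15 = 1.16; spread about 0.71; critical t = 2.00; simulated rate 13%; p(1 − p) = 0.13 × 0.87 = 11%.

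**All settings, no Triple P effect (%).** The joint columns give significant in Triple P and not in control.

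| n per arm | ρ | s | Independent, within | Independent, joint | Paired, within | Paired, joint |
|---|---|---|---|---|---|---|
| 30 | 0.5 | 0.2 | 5 | 5 | 19 | 15 |
| 30 | 0.5 | 0.3 | 13 | 11 | 36 | 23 |
| 30 | 0.5 | 0.4 | 27 | 20 | 56 | 25 |
| 30 | 0.7 | 0.2 | 2 | 2 | 28 | 20 |
| 30 | 0.7 | 0.3 | 8 | 8 | 54 | 25 |
| 30 | 0.7 | 0.4 | 23 | 17 | 78 | 17 |
| 50 | 0.5 | 0.2 | 9 | 8 | 28 | 20 |
| 50 | 0.5 | 0.3 | 26 | 19 | 55 | 25 |
| 50 | 0.5 | 0.4 | 51 | 25 | 79 | 16 |
| 50 | 0.7 | 0.2 | 5 | 4 | 43 | 25 |
| 50 | 0.7 | 0.3 | 20 | 16 | 77 | 18 |
| 50 | 0.7 | 0.4 | 52 | 25 | 95 | 5 |

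Ranges: independent 2–52% within and 2–25% joint; paired 19–95% within and 5–25% joint. Simulation of the paired joint event can show values up to 26%, which is sampling noise around the 25% ceiling.

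**Zero-shift check (s = 0).** The paired test rejects in about 5% of trials. The independent test rejects in under 1%: in large samples its effective cut-off is 1.96 / √0.5 = 2.77 or 1.96 / √0.3 = 3.58.

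**Between-group test on change scores.** About 5% in every setting, whatever the value of s.

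**The case against.** The strongest reply is that the valid analysis is already in the plan. The difference in mean change is the only comparison tied to impact against standard care, and the controls were tested for a comparative purpose. This stands, and it limits the point to the role of the within-group result.

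A reader might infer that the plan will call Triple P effective on a within-group result alone, or will compare the two arms' p-values. The documents support neither. No rule makes a within-group result sufficient, and none excludes it.

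Other parts of the reply also stand.

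- The paired rates apply to a test the plan does not name. For the independent t-test as written the rates are lower, and three of the twelve settings, all with a 0.2 SD shift, are at or below about 5%.
- The size of the shared shift is assumed.
- Regression to the mean needs selection on high scores, and no such entry rule is given.
- The statement that the children were on medication comes from the Pilot Testing section; extending it to the whole sample is an inference.
- The 5% rate for the between-group test presumes comparable arms. The text available does not describe how mothers were allocated to arms.

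The reply does not remove the gap. The within-group test is still listed under effectiveness at 0.05 with no limit to description. Replacing the independent t-test by a paired one would not close the gap either: in the worked example it raises the rate from 13% to 36%.

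**Conclusion.** The concern holds as a gap in the decision rule. The plan specifies the right contrast, but leaves beside it an uncontrolled test labelled as an effectiveness analysis, with no statement of which governs.

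The size depends on a shared shift that the documents do not quantify. Under the assumptions shown, a within-group test could be significant without any Triple P effect in anything from about 2% to 52% of trials with the test as written. With no shared shift there is no excess. These figures show what the wording permits and do not predict this trial's result.

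It should be fixed. It is not a fatal flaw, because the controlled comparison is already specified and the data for it are collected.

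**What to change.** Reword the Data Analysis section along these lines: *The conclusion on the effectiveness of Triple P rests, for each outcome, solely on the between-group difference in mean change, reported with its 95% CI. Within-group changes (mean change, 95% CI) are reported descriptively for both arms. No conclusion on effectiveness is drawn from them or from comparing their p-values.*

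The sentence on primary analyses should also say that the changes in the three domains are compared between groups.

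The cost is a short rewording, with no new data and no new analysis. The plan is written in the past tense; if the analyses are already done, the same rule can govern how they are reported. The downside is that significant within-group p-values can no longer be cited as support for effectiveness.

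### The plan can be read as testing each domain between arms twice, on unadjusted scores and on mean change, without saying which test decides

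*Combined protocol and SAP*

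**What the plan says.** All the relevant text is in the Data Analysis section of the combined protocol and SAP, apart from two remarks under Pilot Testing.

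- On effectiveness: "The effectiveness of the Triple P intervention was analyzed by comparing pre- and post-intervention scores within and between groups", with independent t-tests as the method. What is compared is scores, and one of the comparisons is between groups.
- A later sentence gives a second quantity: "Differences in mean change scores between the two groups were used to assess the impact of the intervention relative to standard care".
- Between these two stands "The primary analyses focused on evaluating changes in parenting practices, parental competence, and child behavior". It names three domains and refers to changes, but it names no test.
- One significance level, 0.05 two-sided, applies throughout, with no division across tests or domains.
- Baseline is handled by testing: "To assess baseline equivalence between the intervention and control groups, independent samples *t*-tests were performed on all pre-intervention variables". The section does not say what follows if the arms differ, and it names no baseline-adjusted model.
- The section states that no sensitivity analysis was done.

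Under Pilot Testing, "10 participants were conveniently selected to have the triple p sessions in the pilot study", and the same section has "participants in the pilot included in the study sample". The only random step described is the selection of mothers from a clinic registry. How mothers were assigned to arms is not described.

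**The concern.** A difference in post-test means and a difference in mean change estimate the same effect only if the arms start level on average. Where they do not, the post-test difference includes whatever part of the starting difference is still present at post-test. A gap in favour of the Triple P arm can then look like benefit although both arms changed equally. A gap the other way can hide a real benefit. The supplied text does not describe the random allocation that would make the starting difference zero on average, and keeping ten conveniently selected pilot mothers in the sample makes imbalance plausible.

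Even with level arms, two tests at 0.05 and no rule on which one counts give each domain two chances of a significant result. A reader of the results could not tell whether a reported effect rests on the post-test comparison, the change comparison, or whichever was significant.

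**Working it through.** **Inputs.** From the documents: alpha 0.05 two-sided (critical z = 1.96), three domains, and pre- and post-test scores in both arms. The documents give no arm size, SD, pre-post correlation or expected baseline gap, and no error rate to reproduce beyond the nominal 5%. Assumed: pre-post correlation r from 0.3 to 0.7, equal SDs (set to 1), 30 or 50 mothers per arm, and a 0.3 SD baseline gap.

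**Step 1. How closely the two tests agree.** For one mother, Cov(post, post − pre) = 1 − r and Var(post − pre) = 2(1 − r). The correlation between the two between-arm statistics is therefore (1 − r)/√(2(1 − r)) = √((1 − r)/2).

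**Step 2. No effect and no imbalance.** The chance that at least one test is significant is 1 − P(|Z₁| < 1.96 and |Z₂| < 1.96), with Z₁ and Z₂ bivariate normal at that correlation.

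| r | correlation of the tests | either test significant |
|---|---|---|
| 0.3 | 0.592 | 8.8% |
| 0.5 | 0.500 | 9.1% |
| 0.7 | 0.387 | 9.4% |

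Two independent tests would give 1 − 0.95² = 9.75%, so the positive correlation removes little of the excess. These are two-sided rates. By symmetry the chance of a significant result favouring Triple P is about half, 4.4–4.7%, against 2.5% for one test.

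**Step 3. No effect, and a 0.3 SD gap that persists fully.** The post-test difference is 0.3 SD and the change difference is 0. For the post-test comparison the non-centrality is 0.3 × √(n/2).

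- 30 per arm: 0.3 × √15 = 1.162. The two-sided t-test is significant in 20.8% of trials (21.3% by the normal approximation).
- 50 per arm: 0.3 × √25 = 1.500. It is significant in 31.8% of trials (32.3% by the normal approximation).
- The change-score test stays at 5% at either size.

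**Step 4. No effect, and a chance gap g that regresses.** The expected post-test difference is r × g and the expected change difference is −(1 − r) × g. At r = 0.5 and g = 0.3 these are +0.15 and −0.15 SD. Given such a gap, each difference has SD √(0.75 × 2/n), because 1 − r² = 0.75. Each is judged against 1.96 × √(2/n).

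- 30 per arm: cut-off 0.506, SD 0.224. Both tests are significant in 5.7% of trials.
- 50 per arm: cut-off 0.392, SD 0.173. Both tests are significant in 8.2% of trials.

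Here the change score is no better than the post-test score; it errs in the opposite direction. Adjusting for the pre-test score removes the bias in this scenario.

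**The case against.** The strongest reply is that the second test is inferred. The section never says outright that post-test scores were compared between arms. The sentence on mean change may simply specify the earlier between-group comparison, which would leave one contrast, and the primary-analyses sentence also speaks of changes. On that reading the figures in steps 2 and 3 do not apply. The reading is coherent and cannot be excluded, but the text does not establish it. The effectiveness sentence compares scores, the impact sentence compares changes, and nothing links or ranks them.

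A reader might infer three stronger things that the documents do not support.

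- *That a between-arm pre-test comparison serves as evidence of effect.* Those tests have their own sentence and a stated baseline purpose. The mention of pre-test scores under effectiveness can mean pre compared with post.
- *That existing differences inflate the benefit.* Nothing shows which arm started better, so the bias could run either way.
- *That the change score is the cure.* Its 5% holds only if the gap persists fully, as step 4 shows.

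It is also fair to say that the text looks like an extract and that allocation may be described elsewhere. The point therefore rests on what the supplied text leaves out and does not assert that the trial was not randomised. Even with randomisation, the excess in step 2 would remain if either test suffices.

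**Conclusion.** The concern holds in a limited form. On the ordinary reading there are two between-arm tests per domain at 0.05 and no explicit rule on which decides. The lean towards change in the primary-analyses sentence is not such a rule.

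If either test suffices, the two-sided error per domain is about 8.8–9.4% instead of 5%. This rests on equal SDs and a pre-post correlation of 0.3–0.7. The 21% and 32% figures illustrate one scenario, with an assumed gap, full persistence and assumed arm sizes; they do not predict what happens in this trial. The documents do not support saying that a raw post-test comparison was certainly used, or that any resulting error favours Triple P. They do support saying that the plan as written permits a wrong conclusion in either direction, and that pre-test scores already collected in both arms allow a better-defined analysis.

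**What to change.** - State that one between-arm contrast per domain decides. The preferred choice is the baseline-adjusted difference: ANCOVA of the post-test score, or equivalently of change, on arm and pre-test score.
- Give the unadjusted difference in mean change as supportive. If the arms were not randomised, note that the two estimates can differ and report both.
- Show post-test means and SDs by arm without a p-value.
- State that between-arm comparisons of pre-test scores describe baseline only.

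This settles the choice of test within a domain. With three domains at 0.05 each, treated as independent, the chance of at least one false positive is still 1 − 0.95³ = 14.3%. A single primary outcome or a multiplicity rule is a separate decision.

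The cost is wording and one standard model per domain, with no new data. There are two downsides. A result significant only on the raw post-test comparison can no longer be cited as evidence. The section is also written in the past tense, so if the data have already been analysed, the choice of deciding contrast must be reported as post hoc.
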